## F 4 Follow-up

### F 4.1 Potential Hy's Law Criteria Not Met

If the participant does not meet PHL criteria the investigator will:

- Inform the AstraZeneca representative that the participant has not met PHL criteria.
- Perform follow-up on subsequent laboratory results according to the guidance provided in the CSP.

### F 4.2 Potential Hy's Law Criteria Met

If the participant does meet PHL criteria the investigator will:

- Notify the AstraZeneca representative who will then inform the central Study Team.
- Within 1 day of PHL criteria being met, the investigator will report the case as a SAE of PHL; serious criteria 'Important medical event' and causality assessment 'yes/related' according to CSP process for SAE reporting.
- For participants that met PHL criteria prior to starting IMP, the investigator is not required to submit a PHL SAE unless there is a significant change# in the participant's condition.
- The Study Physician contacts the investigator, to provide guidance, discuss and agree an approach for the study participants' follow-up (including any further laboratory testing) and the continuous review of data.
- Subsequent to this contact the investigator will:
  - Monitor the participant until liver biochemistry parameters and appropriate clinical symptoms and signs return to normal or baseline levels, or as long as medically indicated. Complete follow-up SAE Form as required.
  - Investigate the etiology of the event and perform diagnostic investigations as discussed with the Study Physician. This includes deciding which of the tests available in the HL lab kit should be used.
  - Complete the 3 Liver eCRF Modules as information becomes available.

#A 'significant' change in the participant's condition refers to a clinically relevant change in any of the individual liver biochemistry parameters (ALT, AST, or TBL) in isolation or in combination, or a clinically relevant change in associated symptoms. The determination of whether there has been a significant change will be at the discretion of the investigator, this may be in consultation with the Study Physician if there is any uncertainty.

## F 5      Review and Assessment of Potential Hy's Law Cases

The instructions in this Section should be followed for all cases where PHL criteria are met.

As soon as possible after the biochemistry abnormality was initially detected, the Study Physician contacts the investigator in order to review available data and agree on whether there is an alternative explanation for meeting PHL criteria other than DILI caused by the IMP, to ensure timely analysis and reporting to health authorities within 15 calendar days from date PHL criteria was met. The AstraZeneca Global Clinical Lead or equivalent and Global Safety Physician will also be involved in this review together with other subject matter experts as appropriate.

According to the outcome of the review and assessment, the investigator will follow the instructions below.

**Where there is an agreed alternative explanation** for the ALT or AST and TBL elevations, a determination of whether the alternative explanation is an AE will be made and subsequently whether the AE meets the criteria for a SAE:

- If the alternative explanation is **not** an AE, record the alternative explanation on the appropriate eCRF.
- If the alternative explanation is an AE/SAE: update the previously submitted PHL SAE and AE eCRFs accordingly with the new information (reassessing event term; causality and seriousness criteria) following the AstraZeneca standard processes.

If it is agreed that there is **no** explanation that would explain the ALT or AST and TBL elevations other than the IMP:

- Send updated SAE (report term 'Hy's Law') according to AstraZeneca standard processes.
  - The 'Medically Important' serious criterion should be used if no other serious criteria apply.
  - As there is no alternative explanation for the HL case, a causality assessment of 'related' should be assigned.

If, there is an unavoidable delay of over 15 calendar days in obtaining the information necessary to assess whether or not the case meets the criteria for HL, then it is assumed that there is no alternative explanation until such time as an informed decision can be made:

- Provides any further update to the previously submitted SAE of PHL, (report term now 'Hy's Law case') ensuring causality assessment is related to IMP and seriousness criteria is medically important, according to CSP process for SAE reporting.

- Continue follow-up and review according to agreed plan. Once the necessary supplementary information is obtained, repeat the review and assessment to determine whether HL criteria are still met. Update the previously submitted PHL SAE report following CSP process for SAE reporting, according to the outcome of the review and amending the reported term if an alternative explanation for the liver biochemistry elevations is determined.

## **F 6        Actions Required When Potential Hy's Law Criteria are Met Before and After Starting Study Intervention**

This section is applicable to participants who meet PHL criteria on study intervention, having previously met PHL criteria at a study visit prior to starting study intervention.

At the first on-study intervention occurrence of PHL criteria being met the investigator will determine if there has been a **significant change** in the participants' condition# compared with the last visit where PHL criteria were met#.

- If there is no significant change no action is required.
- If there is a significant change, notify the AstraZeneca representative, who will inform the central Study Team, then follow the subsequent process described in Section [F 4.2](#).

# A 'significant' change in the participant's condition refers to a clinically relevant change in any of the individual liver biochemistry parameters (ALT, AST, or TBL) in isolation or in combination, or a clinically relevant change in associated symptoms. The determination of whether there has been a significant change will be at the discretion of the investigator, this may be in consultation with the Study Physician if there is any uncertainty.

## F 7        Laboratory Tests

### Hy's Law Lab Kit for Central Laboratories

Additional standard chemistry and coagulation tests	GGT
	LDH
	Prothrombin time
	INR
Viral hepatitis	IgM anti-HAV
	HBsAg
	IgM and IgG anti-HBc
	HBV DNA a
	IgG anti-HCV
	HCV RNA b
	IgM anti-HEV
Other viral infections	HEV RNA
	IgM & IgG anti-CMV
	IgM & IgG anti-HSV
Alcoholic hepatitis	IgM & IgG anti-EBV
	Carbohydrate deficient transferrin (CD-transferrin)
Autoimmune hepatitis	Antinuclear antibody (ANA)
	Anti-Liver/Kidney Microsomal Ab (Anti-LKM)
	Anti-Smooth Muscle Ab (ASMA)
Metabolic diseases	alpha-1-antitrypsin
	Ceruloplasmin
	Iron
	Ferritin
	Transferrin
	Transferrin saturation

a    HBV DNA is only recommended when IgG anti-HBc is positive

b    HCV RNA is only recommended when IgG anti-HCV is positive or inconclusive

## F 8 Recommended Stopping Criteria

**Table F9 Recommended Stopping Criteria and Dose Adaptations for Possible Hepatocellular DILI in Phase II-III NASH Clinical Trials in Participants with Normal or Elevated Baseline ALT ( $> 1.5 \times \text{ULN}$ )a**

Treatment Emergent ALT Elevations	TBL Values at Time of Treatment Emergent ALT Elevation	Presence of Liver-related Symptoms b	Action
NASH Participants with Near Normal ALT at Baseline c			
$\geq 3 \times \text{ULN}$ but $< 5 \times \text{ULN}$	$< 2 \times \text{ULN}$ Participants with Gilbert's syndrome: direct bilirubin $< 2 \times$ baseline AND INR $\leq 1.5$	Absent	Repeat ALT, AST, ALP, TBL in 2-3 days. Follow-up for symptoms.
		Present	Repeat ALT, AST, ALP, TBL in 2-3 days. Follow-up for symptoms. Initiate evaluation for other etiologies of abnormal liver tests.
$\geq 5 \times \text{ULN}$ but $< 8 \times \text{ULN}$	$TBL \geq 2 \times \text{ULN}$ Participants with Gilbert's syndrome: direct bilirubin $\geq 2 \times$ baseline or INR $> 1.5$	Irrespective of symptoms	Interrupt study drug. Initiate close monitoring and workup for competing etiologies. Study drug can be restarted only if another etiology is identified, and liver enzymes return to baseline.
		Absent	Repeat ALT, AST, ALP, TBL in 2-3 days. Follow-up for symptoms. Initiate evaluation for other etiologies of abnormal liver tests.
		Present	Interrupt study drug. Initiate close monitoring and workup for competing etiologies. Study drug can be restarted only if another etiology is identified, and liver enzymes return to baseline.
$\geq 8 \times \text{ULN}$	$TBL \geq 2 \times \text{ULN}$ Participants with Gilbert's syndrome: direct bilirubin $\geq 2 \times$ baseline or INR $> 1.5$	Irrespective of symptoms	Interrupt study drug. Initiate close monitoring and workup for competing etiologies. Study drug can be restarted only if another etiology is identified, and liver enzymes return to baseline.
	Irrespective of TBL	Irrespective of symptoms	Interrupt study drug. Initiate close monitoring and workup for competing etiologies. Study drug can be restarted only if another etiology is identified, and liver enzymes return to baseline.
NASH Participants with Elevated ALT at Baseline c			
$\geq 2 \times \text{baseline}$ but $< 3 \times \text{baseline}$ AND ( $< 300 \text{ U/L}$ )	$< 2 \times \text{ULN}$ Participants with Gilbert's syndrome: direct bilirubin $< 2 \times$ baseline AND INR $\leq 1.5$	Absent	Repeat ALT, AST, ALP, TBL in 2-3 days. Follow-up for symptoms.
		Present	Repeat ALT, AST, ALP, TBL in 2-3 days. Follow-up for symptoms.

**Table F9 Recommended Stopping Criteria and Dose Adaptations for Possible Hepatocellular DILI in Phase II-III NASH Clinical Trials in Participants with Normal or Elevated Baseline ALT ( $> 1.5 \times$  ULN)a**

Treatment Emergent ALT Elevations	TBL Values at Time of Treatment Emergent ALT Elevation	Presence of Liver-related Symptoms b	Action
			Initiate evaluation for other etiologies of abnormal liver tests.
	TBL $\geq 2 \times$ ULN Participants with Gilbert's syndrome: direct bilirubin $\geq 2 \times$ baseline or INR $> 1.5$	Irrespective of symptoms	Interrupt study drug. Initiate close monitoring and workup for competing etiologies. Study drug can be restarted only if another etiology is identified, and liver enzymes return to baseline.
( $\geq 3 \times$ baseline but $< 5 \times$ baseline AND $< 500$ U/L) or ( $\geq 300$ U/L AND $< 500$ U/L AND $< 5 \times$ baseline)	< $2 \times$ ULN Participants with Gilbert's syndrome: direct bilirubin $< 2 \times$ baseline AND INR $\leq 1.5$	Absent	Repeat ALT, AST, ALP, TBL in 2-3 days. Follow-up for symptoms. Initiate evaluation for other etiologies of abnormal liver tests.
		Present	Interrupt study drug. Initiate close monitoring and workup for competing etiologies. Study drug can be restarted only if another etiology is identified, and liver enzymes return to baseline.
	TBL $\geq 2 \times$ ULN Participants with Gilbert's syndrome: direct bilirubin $\geq 2 \times$ baseline or INR $> 1.5$	Irrespective of symptoms	Interrupt study drug. Initiate close monitoring and workup for competing etiologies. Study drug can be restarted only if another etiology is identified, and liver enzymes return to baseline.
$\geq 5 \times$ baseline or $\leq 500$ U/L	Irrespective of TBL	Irrespective of symptoms	Interrupt study drug. Initiate close monitoring and workup for competing etiologies. Study drug can be restarted only if another etiology is identified, and liver enzymes return to baseline.

a Adapted from: (Regev et al 2019)

b Liver-related symptoms include: severe fatigue, nausea, vomiting, right upper quadrant pain

c Baseline ALT is derived from an average of 2 pretreatment ALT measurements at least 2 weeks apart.

Elevated baseline is defined as ALT  $\geq 1.5 \times$  ULN. If on treatment a participant has 2 or more consecutive ALT values, at least 2 weeks apart, each less than 50% of the baseline ALT with any 2 consecutive values being within 40% of each other (with percentage calculated based on the larger value as the denominator), then a new baseline should be set to be the minimum of the latest consecutive pair of values that are "stable" (ie, within 40% of each other).

[figure not shown]
ALP, alkaline phosphatase; ALT, alanine aminotransferase; AST, aspartate aminotransferase; DILI, drug-induced liver injury; INR, international normalized ratio; NASH, non-alcoholic steatohepatitis; TBL, total bilirubin; ULN, upper limit of normal

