#### **Diagnostic Assessments**

- 29 Abnormal laboratory values including any of the following:
  - (a) AST or ALT > 5 × ULN.
  - (b) ALP  $\geq$  1.5 × ULN, unless not of hepatic origin.

- (c) Impaired renal function defined as estimated glomerular filtration rate  $\leq 30 \text{ mL/minute}/1.73 \text{ m}^2$  at screening (estimated according to chronic kidney disease epidemiology collaboration) ([Inker et al 2021](#)).
- (d) Albumin  $< 35 \text{ g/L}$ .
- (e) International normalized ratio  $> 1.3$ .
- (f) TBL  $> \text{ULN}$  in the absence of known Gilbert's disease.
- (g) Platelets  $< 150000/\text{mm}^3$ .
- (h) MELD score  $\geq 12$ .
- (i) Any other clinically significant abnormalities in clinical chemistry, hematology, or urinalysis results as judged by the investigator.
- 30 Severely uncontrolled hypertension defined systolic BP  $\geq 180 \text{ mmHg}$  and/or diastolic BP  $\geq 110 \text{ mmHg}$  on the average of 2 supine measurements after being at rest for at least 10 minutes at screening or randomization.
- 31 Heart rate  $> 110 \text{ bpm}$  or  $< 50 \text{ bpm}$  at randomization.
- 32 Any clinically significant abnormalities in rhythm, conduction, or morphology of the resting ECG, as considered by the investigator at the screening visit (Visit 1) and/or on Week -1.

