- AE or other safety reasons as judged by the investigator and/or sponsor, where continued treatment may put the participant at undue risk
- Development of uncontrolled and clinically significant **CCI** as judged by the investigator
- Severe non-compliance with the CSP
- Elevations in liver tests corresponding to possible DILI (Appendix [F 8](#) for details)

Data to be collected at the time of intervention discontinuation and follow-up and any further evaluations that need to be completed are noted in [Table 2](#).

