## **Appendix F Actions Required in Cases of Increases in Liver Biochemistry and Evaluation of Hy's Law**

### **F 1 Introduction**

This Appendix describes the process to be followed in order to identify and appropriately report Potential Hy's Law (PHL) cases and Hy's Law (HL) cases. It is not intended to be a comprehensive guide to the management of elevated liver biochemistries.

Specific guidance on stopping criteria and dose adaptations in possible hepatocellular drug-induced liver injury (DILI) and in possible cholestatic DILI can be found in Appendix F 8 of the CSP.

During the course of the study the investigator will remain vigilant for increases in liver biochemistry. The investigator is responsible for determining whether a participant meets potential PHL criteria at any point during the study.

All sources of laboratory data are appropriate for the determination of PHL and HL events; this includes samples taken at scheduled study visits and other visits including central and all local laboratory evaluations even if collected outside of the study visits; for example, PHL criteria could be met by an elevated alanine aminotransferase (ALT) from a central laboratory and/or elevated total bilirubin (TBL) from a local laboratory.

The investigator will also review adverse event (AE) data (for example, for AEs that may indicate elevations in liver biochemistry) for possible PHL events.

The investigator participates, together with AstraZeneca clinical project representatives, in review and assessment of cases meeting PHL criteria to agree whether HL criteria are met. HL criteria are met if there is no alternative explanation for the elevations in liver biochemistry other than DILI caused by the IMP.

The investigator is responsible for recording data pertaining to PHL/HL cases and for reporting serious adverse events (SAEs) and AEs according to the outcome of the review and assessment in line with standard safety reporting processes.

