#### **Central Laboratories Being Used:**

When a participant meets any of the PHL identification criteria, in isolation or in combination, the central laboratory will immediately send an alert to the investigator (also sent to AstraZeneca representative).

The investigator will also remain vigilant for any local laboratory reports where the PHL identification criteria are met, where this is the case the investigator will:

- Notify the AstraZeneca representative.
- Request a repeat of the test (new blood draw) by the central laboratory without delay.
- Complete the appropriate unscheduled laboratory eCRF module(s) with the original local laboratory test result.

When the identification criteria are met from central or local laboratory results the investigator will without delay:

- Determine whether the participant meets PHL criteria (definition in Section F 2) by reviewing laboratory reports from all previous visits (including both central and local laboratory results).

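### Table F9, elevated-baseline participants: the highest interruption row reads at or below 500 U/L where the other rows require at or above 500 U/L

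*Protocol*

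**What the plan says.** Table F9 in Protocol Appendix F 8 sets out actions for possible hepatocellular drug-induced liver injury. Its first column is headed "Treatment Emergent ALT Elevations", so it concerns rises on treatment. For participants with elevated baseline ALT there are three tiers, in rising order of severity:

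- **Tier 1:** ALT from 2 to below 3 × baseline and below 300 U/L. If total bilirubin is below 2 × ULN, the tests are repeated and drug continues.
- **Tier 2:** ALT at least 3 × "baseline but $< 5 \times$ baseline AND $< 500$ U/L", or from 300 to below 500 U/L while below 5 × baseline. If bilirubin is below 2 × ULN and there are no symptoms, the tests are repeated, other causes are evaluated and drug continues.
- **Last row:** "\geq 5 \times$ baseline or $\leq 500$ U/L". Drug is interrupted whatever the bilirubin and whether or not symptoms are present.

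Section 7.1 lists "Elevations in liver tests corresponding to possible DILI" among the grounds for stopping study intervention and points to Appendix F 8 for details. Appendix F 1 also names F 8 as the place for the specific stopping guidance.

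**The concern.** The tiers climb to below 300 U/L and then to below 500 U/L, so the last row should begin where the second ends. As supplied, its absolute limit runs downwards from 500 U/L. This creates two faults: values meant for repeat testing also trigger interruption, and some values worse than Tier 2 have no instruction.

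The second fault matters more. Within this stratum, the last row is the only one meant to require interruption on ALT alone. The other safeguards do not replace it. At ALT of 3 × ULN or more, "the central laboratory will immediately send an alert to the investigator", but the alert prompts review, not interruption. Potential Hy's Law also needs bilirubin of at least 2 × ULN. Where those criteria are not met, Appendix F 4.1 tells the investigator to "Perform follow-up on subsequent laboratory results according to the guidance provided in the CSP", which leads back to this table.

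**Working it through.** Write *b* for baseline ALT and *a* for on-treatment ALT, both in U/L.

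**Inputs**
- Tier and last-row limits: Table F9, elevated-baseline stratum.
- Elevated baseline: at least 1.5 × ULN (Table F9 footnote).
- Entry cap: Section 5.2, criterion 29(a), excludes "AST or ALT > 5 × ULN".
- ULN: the current criteria give no value. I assume 41 U/L (men) and 31 U/L (women), the figures in the superseded ALT inclusion criterion listed in the amendment summary.

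**Overlap.** All Tier 1 and Tier 2 values are below 500, so all satisfy *a* ≤ 500 and also meet the last row. Example: *b* = 80 and *a* = 170 gives 170/80 = 2.1 × baseline. With bilirubin below 2 × ULN and no symptoms, Tier 1 says repeat the tests; the last row says interrupt.

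**Gap.** A value is in no row when *a* > 500 and *a* < 5*b*. This needs 5*b* > 500, that is *b* > 100.

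| Baseline (U/L) | 5 × baseline | ALT values in no row (whole U/L) |
|---|---|---|
| 100 | 500 | none |
| 101 | 505 | 501–504 |
| 120 | 600 | 501–599 |
| 150 | 750 | 501–749 |
| 205 | 1025 | 501–1024 |

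At baseline 150, an ALT of 400 meets the interruption row (and Tier 2), 600 (4 × baseline) meets nothing, and 750 meets the interruption row again.

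**Is *b* > 100 eligible?** Entry allows ALT up to 5 × ULN, so it is eligible for any ULN above 100/5 = 20 U/L. Under the assumed ULNs the cap is 5 × 41 = 205 or 5 × 31 = 155 U/L. A baseline of 100 U/L is then 100/41 = 2.4 × ULN or 100/31 = 3.2 × ULN.

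**Full grid.** Take whole-number baselines from 47 (1.5 × 31 = 46.5, rounded up) to 205, and ALT from 1 to 1500, keeping *a* ≥ 2*b* or *a* > 500. Since 2*b* never exceeds 410, the first condition covers the second.

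- Cells: Σ(1501 − 2*b*) = 159 × 1501 − 2 × 20,034 = 198,591.
- In more than one row, as printed: 3*b* values for each *b* from 47 to 100 (total 11,907), and 500 − 2*b* values for each *b* from 101 to 150 (12,450) and from 151 to 205 (7,920). The sum is 32,277.
- In no row, as printed: Σ(5*b* − 501) over *b* = 101 to 205 = 80,325 − 52,605 = 27,720.
- With *a* ≥ 500 in the last row: 0 overlaps and 0 gaps.

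Dropping the *a* ≥ 2*b* restriction adds the Tier 2 values from 300 up to 2*b* − 1 at baselines above 150: Σ(2*b* − 300) over *b* = 151 to 205 = 3,080. That gives 32,277 + 3,080 = 35,357 Tier 1 or Tier 2 cells, all of which also meet the last row as printed.

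These counts show the logic of the table. They are not probabilities of an event.

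**The case against.** **The sign may be an extraction error.** The point rests on one inequality in a machine-read table, and the near-normal part of that table looks disturbed: its 5 to 8 × ULN tier has lost its low-bilirubin cell and row labels appear shifted. The elevated-baseline definition also varies between ≥ and > 1.5 × ULN in otherwise similar footnotes, although that could be the sponsor's own inconsistency. Figure F3 restates the criteria for this stratum and cannot be seen. This objection stands as a limit on confidence, and it makes a source check the first step. Against it, the other signs in this stratum read sensibly. If the figure is right, the table still conflicts with it.

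**Nobody would apply the literal reading.** It would make both milder tiers pointless, and the near-normal stratum ends in an open upper band at 8 × ULN, so most investigators would probably infer at or above 500 U/L. That is fair and lowers the practical risk. It does not justify leaving a stopping threshold to inference at approximately 48 sites.

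**Other routes to stopping exist.** Section 7.1 allows discontinuation on the safety judgment of the investigator or sponsor, and Section 8 calls for immediate safety concerns to be discussed with the sponsor. The alert also reaches the sponsor's representative, the 5 × baseline limb is unaffected, and the criteria are headed as recommendations. These limit the harm, but none supplies the missing threshold.

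**Conclusion.** The concern holds on the supplied text. The last elevated-baseline row contradicts both milder tiers. It also leaves ALT above 500 U/L but below 5 × baseline without an instruction for any baseline above 100 U/L, a gap that widens to 501–1024 U/L at a baseline of 205 U/L. The gap does not depend on the assumed ULNs; only the upper end of the eligible baseline range does.

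Confidence is medium because the printed page and Figure F3 could not be inspected. The documents give no basis for estimating how often ALT would fall in the gap. The point concerns a participant-level safety rule and should be fixed; the primary analysis and sample size are not affected.

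**What to change.** 1. Check the source page of Table F9 and Figure F3.
2. If the table prints the sign as supplied, change the last elevated-baseline row to ALT at least 5 × baseline or at least 500 U/L. The limits on Tier 2 already determine this threshold.
3. Make Figure F3 agree with the corrected row and notify sites.

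The cost is a one-sign protocol clarification and a site notice. No extra data, visits or participants are needed.
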